#### Research Procedures/Interventions:

**C.1. Overview.** In this single-arm pilot study, we will enroll a consecutive cohort of up to 50 Veterans identified as frail using a standardized frailty assessment and scheduled for major cardiothoracic surgery at the VA Pittsburgh Healthcare System. The 3-6 week long prehabilitation regimen will include: (a) aerobic conditioning, (b) strength and coordination training, (c) respiratory muscle training, and (d) nutritional coaching and supplementation. Pre- and post-prehabilitation assessments will include: (a) frailty; (b) physical function; (c) pulmonary function; (d) nutrition; and (e) health-related quality of life. Using physical performance tests, biomarkers, chart review, survey instruments, and patient logs, we will assess the feasibility of the recruitment, randomization, retention and assessment procedures, compensating patients for their time. Prehabilitation will not last more than 4 weeks for CABG patients. However, for non-cardiac thoracic patients, prehabilitation may be extended out to 6 weeks if the surgeon and patient so choose.

**C.2. Eligibility criteria.** We will recruit frail patients (i.e., RAI $\geq$ 16 and Physician /Provider request for patient with RAI<16) scheduled for a CABG or Valve Surgery. Major non-cardiac thoracic surgery is defined according to VA Surgical Quality Improvement Program (VASQIP) criteria that include cases requiring general, epidural, or spinal anesthesia. It includes 193 unique CPT codes ranked by complexity (26 standard, 146 intermediate, and 21 complex) and excludes 58 low risk “minor” surgical procedures with limited morbidity (e.g., bronchoscopy, percutaneous lung biopsy). From these major surgeries, we will include those procedures that deliberately violate the visceral or parietal pleura with something larger than an 18 gauge needle. For example, we will include lung and esophagus resections of all kinds, but exclude thoracentesis. Exclusion criteria are designed to ensure participant safety in prehabilitation exercises (e.g., low-risk, stable cardiac disease without significant symptoms, arrhythmias, hemodynamic instability or critical coronary lesions). Based on historical data, we expect 2/3rds of eligible

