patients to exhibit mild frailty (RAI 16-25) with essentially intact independence and capacity for prehabilitation. Higher degrees of frailty may impose barriers to full participation, but characterizing those limitations is an important component of this pilot. We will stratify enrollment to ensure approximately equal enrollment of cardiac and non-cardiac thoracic patients.

**C.3. Prehabilitation procedures.** Prehabilitation will last 3-6 weeks—a time frame that does not delay surgery, corresponds to the typical lag for surgical scheduling, and strikes a pragmatic balance between improving physiologic reserve without unduly delaying definitive surgical therapy. Although the training intervention is only 3-6 weeks, studies repeatedly demonstrate neuromuscular strengthening, diminished inflammation, and respiratory improvements within this time. Further, the program also fosters continuity between preoperative training and traditional postoperative rehabilitation, facilitating rapid mobilization and progressive exercise after surgery. Strategies like this enhance functional recovery and reduce the risks of subsequent episodes of disability (e.g., readmission or loss of independence). If clinical contexts such as neoadjuvant chemotherapy or worsening angina require shorter (or permit longer) durations of training, we will examine these events in order to inform the optimal duration of prehabilitation for a larger clinical trial.

**(a) Safety.** Prehabilitation will begin in a telemetry-monitored, hospital-based setting to train patients in the home-based exercises and establish safe targets of exertion. If and as safety is established, exercise will shift to the home with weekly telephone/ VA Video Connect contact to ensure safety and reinforce technique. Remote telephone and VA Video Connect monitoring will be enhanced by the relationships, familiarity, and trust established during the hospital-based sessions. Although safety concerns will require some patients to complete all exercise in monitored, hospital-based settings, we anticipate that many patients will safely transition to home-based exercise after 1-4 hospital-based sessions. Study staff will initiate withdrawal procedures for patients who demonstrate insufficient cognitive or physical capacity to safely carry out the prescribed activities.

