**(c) Ascertain the feasibility of measuring changes over time in frailty, physical function, pulmonary function, nutrition, and health-related quality of life at baseline, the day of surgery, and 30 and 90 days after surgery [Aim 2].** We will summarize the time required to complete each assessment as well as the completeness of data, estimating completion rates with CIs. Graphical analyses will assess simple changes in frailty, physical performance, pulmonary function, nutrition and quality of life over the study period. Although sample size will limit model fit, we will prepare analyses for the larger trial by developing simple mixed models to explore changes over time (baseline and every other week up to the day of surgery, and then 30 and 90 days after). Separate models for each outcome will assess changes, including a fixed effect for time and a random effect for subject. The type of mixed model will depend on the outcome variable with linear mixed models for continuous variables (e.g., RAI, SPPB, 6MWT, MIP, MEP, etc) and generalized mixed models for ordinal/categorical variables (e.g., SGA, frailty phenotype). We will also explore dose-response relationships based on the actual duration of and adherence to the training regimen.

**(d) Explore changes in postoperative mortality, major complications, length of hospital stay, and level of independent living using case-matched historical controls [Exploratory Aim].** We will match each participant to an historical control using local VASQIP data. VASQIP data include variables sufficient to calculate the RAI as well as details about the patient's procedure, comorbidities, outcomes, and a highly reliable prediction of postoperative 30-day mortality. Each historical control will be chosen from VAPHS VASQIP data from the 2 years prior to the study start and matched to the enrolled participant based on procedure, age, RAI score, and VASQIP predicted mortality. We will summarize separately the total number of deaths and major complications at 30 and 90 days for all patients, estimating proportions with associated CIs for the intervention and historical control groups. We will also compute summary statistics (mean, median, standard deviation, range) for length of hospital stay and return to independent living. We will then attempt to assess if differences exist between the groups with regard to these post-operative measures.

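### Training durations changed for clinical reasons cannot show the optimal duration: a slope on received duration or adherence can be confounded by indication, in either direction

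*Combined protocol and SAP*

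**What the plan says.** C.3 names the circumstances in which training will depart from plan: "If clinical contexts such as neoadjuvant chemotherapy or worsening angina require shorter (or permit longer) durations of training". The same sentence gives the use to be made of them: "we will examine these events in order to inform the optimal duration of prehabilitation for a larger clinical trial".

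C.8(c), the analysis for Aim 2, first describes the mixed models: "Separate models for each outcome will assess changes, including a fixed effect for time and a random effect for subject". It then adds: "We will also explore dose-response relationships based on the actual duration of and adherence to the training regimen". No terms are given for that last analysis. The only limitation that C.8(c) names for its models is sample size.

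C.1 makes the permitted duration depend on the operation. For one group, "Prehabilitation will not last more than 4 weeks for CABG patients"; but "for non-cardiac thoracic patients, prehabilitation may be extended out to 6 weeks if the surgeon and patient so choose". C.2 aims for about equal numbers in the two surgical groups: "We will stratify enrollment to ensure approximately equal enrollment of cardiac and non-cardiac thoracic patients". The study has one arm and at most 50 participants, so duration is received and not assigned.

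**The concern.** A duration that changes because the patient's condition or treatment changed is not a neutral dose. Worsening angina can shorten training and also reduce walking distance on the day of surgery. Chemotherapy can open a longer window for training and also depress function, frailty scores and nutrition. Adherence has the same weakness, since a patient who is getting sicker may train less. In each case the association between dose and outcome can exist with no effect of dose.

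Nothing in the plan separates these cases. The subject effect in the mixed model absorbs stable differences in level between patients. It does not absorb a different trajectory in patients who deteriorate after baseline. The historical-control matching in C.8(d) serves the postoperative outcomes and says nothing about why duration differs among participants.

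What is at stake is a design choice. C.3 states that the information is meant for the training duration of the larger trial. More patients would narrow the interval around a biased slope without moving it.

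**Working it through.** The documents give no effect size, SD or rate for changed durations, so there is no figure of theirs to reproduce. The question is how large a slope can appear when the true effect of duration is zero.

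**Formula.** Let a share *p* of patients worsen, train *d* weeks less on average and do *g* worse on the outcome. Let *v* be the variance of duration from all other sources. The expected slope of outcome on duration is

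b = p(1−p)·d·g / [v + p(1−p)·d²].

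**6-minute walk, in metres per week.** From the documents: n = 50, and 30 m as a clinically significant difference (C.5). Assumed: everything else, including a residual SD of 40 m and uniformly distributed durations, each over a 2-week range, so v = 2²/12 = 0.333.

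- *Separated durations* (worsening patients 1–3 weeks, others 3–5; changes of −30 m and +20 m). Here d = 2 and g = 50.
  - p = 0.1: 0.09·2·50 / (0.333 + 0.09·4) = 9/0.693 = 13.0
  - p = 0.2: 16/0.973 = 16.4
  - p = 0.3: 21/1.173 = 17.9
- *Overlapping durations* (2–4 and 3–5 weeks, 20 m gap). Here d = 1 and g = 20.
  - p = 0.1: 1.8/0.423 = 4.3
  - p = 0.2: 3.2/0.493 = 6.5

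Simulation (4,000 trials per row, true slope 0) gives the sampling SD and tests possible remedies. Cells show mean slope, with sampling SD in brackets.

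| Scenario | Unadjusted | Baseline value and RAI added | Indicator for worsening added | Worsening patients excluded |
|---|---|---|---|---|
| Separated, p = 0.1 | 12.6 (7.7) | 12.6 (7.8) | 0.0 (10.1) | 0.1 (10.6) |
| Separated, p = 0.2 | 16.3 (6.2) | 16.3 (6.4) | 0.0 (10.2) | 0.0 (11.2) |
| Separated, p = 0.3 | 18.0 (5.3) | 18.0 (5.5) | 0.1 (9.9) | 0.0 (11.9) |
| Overlapping, p = 0.1 | 4.1 (9.1) | 4.1 (9.3) | 0.0 (10.1) | 0.1 (10.6) |
| Overlapping, p = 0.2 | 6.5 (8.5) | 6.6 (8.7) | 0.1 (10.2) | 0.2 (11.3) |

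Baseline covariates were generated independently of later worsening. They leave the slope where it was, because here the deterioration arises after baseline. Only separating the worsening patients removes it, and the sampling SD rises to about 10–12.

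**Surgery type, in SD per week.** Take 25 cardiac patients at 3–4 weeks and 25 thoracic patients at 3–6 weeks, uniform. The ranges follow C.1 and C.3, but C.1's 4-week limit names CABG only, so applying it to valve patients is an assumption. Mean durations are 3.5 and 4.5 weeks. The variance is (1/12 + 9/12)/2 + 0.25·1² = 0.667. If thoracic patients do better by 0.5 SD for any other reason, the slope is 0.25·1·0.5/0.667 = 0.19 SD per week. At 1.0 SD it is 0.375.

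**Direction.** In the same two-group setting:

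- If 10–30% of patients worsen, lose 1–2 weeks and score 0.5–1.0 SD worse, the false slope is +0.06 to +0.28 SD per week, with p < 0.05 in 6–60% of simulated trials.
- If chemotherapy adds 2 weeks in 30% of thoracic patients and lowers the outcome by 0.5–1.0 SD, the slope is −0.11 to −0.23 SD per week (15–46% of trials). This lets some durations pass 6 weeks, so it illustrates sign and not a likely size.
- With no confounding, p < 0.05 occurs in 5%.
- With reason for change and surgery type both in the model, the worsening scenarios return a mean slope between −0.006 and +0.006, and p < 0.05 in 4.6–5.6%. This is a best case, because the recorded reason is assumed to capture severity fully.

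**The case against.** The strongest reply is that the plan commits to no such slope. C.3 speaks only of examining events, which may mean describing why training was cut short or could be extended. That is legitimate feasibility information. C.8(c) gives dose-response one exploratory sentence with no model, and no rule ties any estimate to the next trial's duration. This stands in part. A reader might infer that the plan has chosen an unadjusted between-patient regression, or that worsening disease will appear as a benefit of longer training. The documents support neither. They name no model for this step, and the two clinical examples can push in opposite directions. What remains is the stated purpose, which goes beyond description, together with the absence of any handling of the reason for change.

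A second reply is that much of the material is already collected. C.8(c) models the biweekly series, and C.5 provides training logs and barrier interviews. This is correct and makes the remedy cheap. But the interviews are summarised as narrative, and nothing links them to the dose-response analysis. Within-patient gains are also selective, because patients who worsen leave the series and later intervals come from those who stayed well.

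A third reply is that the sizes were chosen. That is also correct. With overlapping durations and a 20 m gap, the false slope is smaller than one sampling SD. The 6-minute walk is itself optional under C.5.

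**Conclusion.** The concern holds in a limited form. Durations altered by clinical events cannot show which duration is best, and a slope on received duration or adherence can be confounded by indication in either direction. Surgery type is a second route to the same bias, because the permitted durations differ.

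The size cannot be derived from the documents, which do not say how many durations will change. The illustrative range of about 4 to 18 m per week, against the 30 m benchmark, rests on assumed shares, gaps, durations and SD. At the low end it would be lost in sampling error. At the high end it could be mistaken for a real effect. The metre-based illustration contains no surgical groups, so it does not establish the size of the bias within either one.

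Because the study is an exploratory single-arm pilot, this does not threaten its feasibility aims. It bears on one stated use of the results, and the plan should be corrected there.

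**What to change.** 1. Record for each participant the planned duration, the actual duration and a coded reason for any change, distinguishing at least clinical worsening, neoadjuvant treatment, and surgeon or patient choice. The Abstract gives a 4-week regimen while C.1 and C.3 give 3–6 weeks. These passages must be reconciled so that a departure from plan has a defined reference.
2. In C.3, replace the statement that these events inform the optimal duration. Say instead that clinically changed cases will be reported descriptively, as feasibility data on which durations are achievable, and that the pilot cannot identify an optimal duration.
3. In C.8(c), present any dose-response analysis by surgery type or adjusted for it, and both with and without patients whose duration was changed for clinical reasons.
4. Baseline values may be added for precision, but the text should not present them as removing this bias.
5. Gains by biweekly interval within patients may be shown, with the number leaving the series at each interval and their reasons.

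The cost is one extra coded field, a few sentences of analysis plan, and wider intervals in the restricted analysis. No training duration is proposed here.

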**Table 1: Assessment Schedule**

	Baseline	Every other Week In-hospital	Day of surgery	30 Days post-op	90 Days post-op
Demographics					
Age, sex, race, ethnicity, etc	X				
Procedure-related variables	X			X	
Living Location	X		X	X	X
Physical Performance					
SPPB	X	X	X		x
MIP & MEP	X	X	X		x
6 Minute Walk Test	X	X	X		X
Frailty (multiple measures)	X	X	X		x
Nutrition					
Prealbumin (biweekly)	X	X	X		x
BMI	X	X	X		x
Subjective Global Assessment	X		X		x
Compliance					
Patient Logs		X	X		
Barrier Assessment	X	X	X	X	X
Outcomes					
Mortality				X	X
Length of Stay				X	
Major Complications (30 day)				X	
Quality of Life	X		X		X
Quality of Surgical Care (Pre)			X		
Quality of Surgical Care (Post)				X	
Measure of Flourishing	X		X		X
Measures of Decision Quality	x		x	X	x

### C.5. Variables Assessed.

- Age, sex, race, ethnicity and socioeconomic status will be assessed by direct patient survey or chart review.
- Procedure-related variables will include the CPT codes of the initially planned operation as well as the operation actually performed. We will also abstract from the chart the type of anesthesia, the duration of the procedure, and the disposition of the patient at the end of surgery (e.g., discharge v. admission)
- Living Location is the environment where patients are living before and after the index operation (i.e., home, nursing home, etc). It will be assessed by direct patient survey or chart review and followed as an outcome.
- Short Physical Performance Battery (SPPB) is a test of balance, gait, strength, and endurance that combines gait speed, repeated chair stands and balance tests that together take less than 5 minutes to complete. Each of the 3 tests are scored on a scale from 0-4 with a combined score ranging from 0-12

with lower scores indicating worse performance. Scores below 8 or 10 are interpreted as poor performance. The SPPB accurately predicts adverse outcomes such as disability, hospitalization, nursing home admission, frailty and mortality, and is becoming the reference standard in rehabilitation literature.

- 6 Minute Walk Test is a standard measure of physical performance that measures the total distance traversed in 6 minutes, measured in meters. Clinically significant differences can be quantified in as little as 30 meters. This is an exploratory measure that will only be administered if time allows. As a pilot study, we aim to determine what kinds of assessments are feasible in this group.
- Maximal Inspiratory & Expiratory Pressures (MIP & MEP) are the standard metrics of respiratory muscle strength and will be measured using the TIRE device described above (D.6c). It has been shown that changes as small as 15 cm H2O can significantly reduce postoperative pulmonary complications and length of stay.
- Frailty will be assessed through several measures because no single measure of frailty captures the breadth of the syndrome. In addition to the RAI described above, we will quantify the Hopkins & Edmonton Frail Scales and independently analyze the gait speed and handgrip strength that is part of the Hopkins Frail Scale. We recently developed a streamlined approach to measuring all of these metrics simultaneously in a parsimonious exercise that takes <5 minutes to administer.
- Hopkins Frail Scale encompasses slowness, weakness, weight loss, low physical activity, and exhaustion with  $\geq 3/5$  criteria required to distinguish frailty. It is the most frequently cited tool shown to predict mortality and disability in large cohorts of community-dwelling elders and surgical patients.
- Edmonton Frail Scale is an 11-item survey that assesses 8 dimensions of frailty. Each item is scored 0, 1, or 2 with higher scores indicating greater frailty. The total score ranges from 0-17 with good inter-rater reliability ( $k = 0.77$ ), moderate internal consistency ( $\alpha=0.62$ ), and strong correlation with a geriatrician's assessment of frailty ( $r=.64$ ,  $p<.001$ ).
- Gait speed is one key measure of frailty that has excellent inter-rater reliability (intraclass coefficient 0.88-0.96) and test-retest reliability (intraclass coefficient 0.86-0.91).
- Handgrip Strength has also been demonstrated to have key utility as an index of frailty. A grip dynamometer will be used, averaging 2 serial assessments from the dominant hand.
- Prealbumin will be measured with standard serological testing. Changes can be detected in days, and it is the best available biomarker of nutrition. However, because prealbumin can function as an acute phase reactant, we will also concurrently measure c-reactive protein as a measure of inflammation and interpret prealbumin as proposed by Jensen, et al.
- Body Mass Index (BMI) will be calculated from height and weight assessed each week at the Cardiac Rehab facility, and is considered the most suitable, objective anthropometric indicator of nutritional status, and changes in BMI have been shown to predict survival in the elderly.
- Subjective Global Assessment of Nutrition (SGA) is the standard approach to nutritional assessment. It evaluates multiple domains of nutrition and reliably categorizes patients into 1 of 4 categories: normal, mild-, moderate- and severely malnourished. We will use the 7-point SGA (See Appendix) because it is sensitive to 1-point changes in as little as 1 month and has excellent inter-rater reliability ( $k=.726$ ).
- Compliance with Prehabilitation. Each patient will receive a prehabilitation log book in which they will record details about their home-based regimen, including the date of training, duration and intensity of exercise, IMT repetitions and threshold pressures, nutritional supplements consumed, dietary intake, and pedometer data (e.g., step counts at the beginning and end of each training session). They will be coached in the use of this log at each hospital session. Data from the logbook will be collected from patients weekly and entered into the database for analysis. In addition, because the pedometer stores 7 days of data, and the exercise physiologists will record daily step counts as a measure of overall activity at each hospital session.

- Barrier Assessment will be conducted through face-to-face or telephone interviews with participants who encounter difficulty with recruitment to, retention in, or adherence with the training regimens. Barriers, including advanced frailty and cognitive deterioration will be described and participants will be asked to propose facilitators that might remove or minimize the barrier in future. Interviews will not be elaborate, but the questions are detailed in the case report forms. No formal qualitative analysis will be conducted, but responses will be collated and summarized by research staff. We will not record responses or attempt to create verbatim transcripts, but instead, the research staff conducting the interviews will summarize patient responses and record those summaries in the case report forms.
- Health-Related Quality of Life will be measured with the Assessment of Quality of Life (AQoL-6D) that includes 20 items on a Guttman scale assessing 6 domains: independent living, mental health, relationships, senses, pain and coping. The utility score ranges from -.04 (state worse than death) to 1.0 (full health). It is sensitive to change with a minimum clinically important difference (MCID) of 0.06.
- Quality of Surgical Care will be measured with the Surgical Care Survey (SCS) that includes subscales for quality of pre-surgical care (11 items), day of surgery (6 items), and postoperative care (12 items).
- Flourishing will be measured by the “Secure Flourish” measure, which is 12 items assessing 6 domains: happiness & life satisfaction, mental & physical health, meaning & purpose, character & virtue, close social relationships, and financial & material stability. All items are scored from 0 to 10. This measure is calculating by summing the scores of all six domains.[96]
- Measures of Decision Quality include Decision Regret (5 items), Patient Centeredness of Care (12 items), Satisfaction with the Process of Decision Making (14 items), Satisfaction with the IMPACT clinic (8 items), Satisfaction with the frailty diagnosis (8 items), satisfaction with the palliative care consult (8 items), and Satisfaction with the surgeon (8 items).
- Mortality. Patients completing the 30- and 90-day surveys will be confirmed alive. For all others, chart review including telephone contact with identified surrogates will confirm vital status and date of death (if deceased).
- Length of Stay will be calculated from the date of surgery to the date of discharge or transfer from the hospital. We will also record the time spent in the intensive care unit. Intervals will be calculated in days.
- Major Complications will be abstracted from the chart according to VASQIP coding rules (Appendix). The presence or absence of each complication will be recorded separately, but analysis will focus on a dichotomous outcome indicating the occurrence of serious, Clavien-Dindo level IV complications. These include deep wound infections, organ space infections, wound disruption, pneumonia, unplanned intubation, pulmonary embolism, mechanical ventilation for >48 hours, progressive renal insufficiency, acute renal failure, stroke, coma, cardiac arrest, myocardial infarction, bleeding in excess of 4 units, deep vein thrombosis, sepsis and C. difficile colitis. This approach to analyzing complications has been shown to correlate with frailty. Co-I and Chief of Surgery [name] has authorized the VASQIP nurse abstractor to use standard VASQIP procedures to code the charts of participating patients.

**Incidental Findings:** If any of these tests generate an incidental finding of sufficient clinical significance to warrant review by the patient's primary care physician (PCP), we send the test results to the PCP and follow up with an encrypted email. We will also telephone the patient within a week to inform the patient of the finding and the planned PCP follow-up.

**C.8. Data Analysis** will focus on the feasibility of both the intervention and the outcome assessments.

**(a) General approach for quantitative data.** We will first explore the data using descriptive statistics (e.g., means, standard deviations, percentiles, ranges) and graphical techniques (e.g., histograms,

scatter plots) to examine key variables to assess distributional assumptions, the existence of outliers and data sparseness. We will try to minimize the amount of data missing due to dropouts, but will use multiple imputation if indicated.

**(b) Assess the feasibility of a novel prehabilitation intervention by estimating rates of recruitment, retention, and adherence to the intervention, and by evaluating barriers to participation [Aim 1].** We will summarize the total number of eligible patients approached, recruited, and retained through the completion of study procedures 90 days postoperatively, estimating proportions as well as associated confidence intervals (CIs). We will then estimate rates of adherence to the prehabilitation intervention, computing overall and exercise-specific rates (and CIs) for the home and hospital portions of the regimen. Finally, we will qualitatively analyze reported barriers to participation with an eye to identifying potential solutions.

**(c) Ascertain the feasibility of measuring changes over time in frailty, physical function, pulmonary function, nutrition, and health-related quality of life at baseline, the day of surgery, and 30 and 90 days after surgery [Aim 2].** We will summarize the time required to complete each assessment as well as the completeness of data, estimating completion rates with CIs. Graphical analyses will assess simple changes in frailty, physical performance, pulmonary function, nutrition and quality of life over the study period. Although sample size will limit model fit, we will prepare analyses for the larger trial by developing simple mixed models to explore changes over time (baseline and every other week up to the day of surgery, and then 30 and 90 days after). Separate models for each outcome will assess changes, including a fixed effect for time and a random effect for subject. The type of mixed model will depend on the outcome variable with linear mixed models for continuous variables (e.g., RAI, SPPB, 6MWT, MIP, MEP, etc) and generalized mixed models for ordinal/categorical variables (e.g., SGA, frailty phenotype). We will also explore dose-response relationships based on the actual duration of and adherence to the training regimen.

**(d) Explore changes in postoperative mortality, major complications, length of hospital stay, and level of independent living using case-matched historical controls [Exploratory Aim].** We will match each participant to an historical control using local VASQIP data. VASQIP data include variables sufficient to calculate the RAI as well as details about the patient's procedure, comorbidities, outcomes, and a highly reliable prediction of postoperative 30-day mortality. Each historical control will be chosen from VAPHS VASQIP data from the 2 years prior to the study start and matched to the enrolled participant based on procedure, age, RAI score, and VASQIP predicted mortality. We will summarize separately the total number of deaths and major complications at 30 and 90 days for all patients, estimating proportions with associated CIs for the intervention and historical control groups. We will also compute summary statistics (mean, median, standard deviation, range) for length of hospital stay and return to independent living. We will then attempt to assess if differences exist between the groups with regard to these post-operative measures.

**(e) Additional exploratory analyses.** Two related pilot studies conducted by the PI use methods similar to those described here (e.g., Pro 1840 & Pro 1754). In particular, these studies collect identical patient reported survey measures and identical physical performance measures. Each study describes analyses of these data to generate reliable estimates of central tendency and dispersion for use in designing future studies. And in the case of this study and Pro 1754, they describe measuring change over time during the pre and post operative period. However, each study has struggled with recruitment leading to smaller than expected sample sizes. Therefore, we plan to transfer de-identified data from Pro 1840 and Pro 1754 into this study to augment the sample size and thereby increase the precision and power

of our estimates. We do not plan or expect data analysis of this augmented sample to differ in any way from that described in 1840 and 1754 and to which the participants gave consent; the only difference is that the value of each participant's data is augmented by joining it to other similar data.

